6.5.1.2 Provisional dose levels

Table 6-2 and Table 6-3 describes the starting dose and the dose levels that may be evaluated during this trial for siremadlin and rineterkib, respectively.

Provisional dose levels for siremadlin Table 6-2

Dose Level	Proposed Daily Dose*	Increment From Previous Dose
- 1**	10 mg	- 50%
1	20 mg	(starting dose)
2	30 mg	50%
3	40 mg	33%

*Additional and/or intermediate dose levels may be added during the course of the study. Cohorts may be added at any dose level below the MTD in order to better understand safety, PK, or PD.

Provisional dose levels for rineterkib Table 6-3

Dose Level	Proposed Daily Dose*	Increment From Previous Dose
- 1**	100 mg	- 50%
1	200 mg	(starting dose)
2	300 mg	50%

*Additional and/or intermediate dose levels may be added during the course of the study. Cohorts may be added at any dose level below the MTD in order to better understand safety, PK, or PD.

6.5.2 Guidelines for dose escalation and determination of RP2D

The maximum tolerated dose (MTD) is the highest drug dosage that is not expected to cause dose-limiting toxicity (DLT) in more than 33% of the treated subjects during the DLT evaluation period. The recommended Phase 2 dose (RP2D) may be chosen with fewer subjects, prior to identification of the MTD and may be lower than the MTD.

^{**}Dose level -1 represents a dose that may be evaluated if de-escalation from the starting dose is required due to toxicity

^{**}Dose level -1 represents a dose that may be evaluated if de-escalation from the starting dose is required due to toxicity.

Siremadlin and rineterkib

For the purpose of dose escalation decisions and determination of RP2D, each cohort in Part 1 of the study will consist of 3 to 6 newly enrolled subjects who will be treated at the specified dose levels. Subjects in the first cohort of siremadlin combined with ruxolitinib will be treated with the starting dose of siremadlin 20 mg QD (Day 1-5 of each 28-day cycle). Subjects in the first cohort of rineterkib combined with ruxolitinib will be treated with the starting dose of rineterkib 200 mg QD.

Subjects must complete a minimum of two cycles of treatment with the minimum safety evaluation and drug exposure (see Section 12.1.3 for details) or have had a DLT within the DLT period to be considered evaluable for dose escalation decisions. Dose escalation decisions and RP2D will occur when the cohort of subjects has met these criteria. If a minimum of 3 subjects are required in a cohort and only 2 of these subjects are evaluable and neither subject has experienced a treatment-related toxicity > CTCAE grade 1, dose escalation decisions may be considered.

Dose escalation decisions will be made by Investigators and Novartis study personnel. Decisions will be based on a synthesis of all relevant data available from all dose levels evaluated in the ongoing study including safety information, DLTs, all CTCAE Grade ≥ 2 toxicity data during Cycle 1 or 2, PK, and PD data from evaluable subjects. The recommended dose for the next cohort of subjects will be guided by the Bayesian logistic regression model (BLRM) with EWOC principle. A subject's ruxolitinib dose is neither escalated nor de-escalated and will remain fixed at the stable dose during the dose-escalation/safety run-in part (Part 1) of the study.

The adaptive Bayesian methodology provides an estimate of all dose levels of the combination agent, which is escalated, that do not exceed the MTD and incorporates all DLT information at all dose levels for this estimation. In general, the next dose will have the highest chance that the DLT rate will fall in the target interval (16-33%) and will always satisfy the EWOC principle. In all cases, the dose for the next cohort will not exceed a 100% increase from the previous dose. Smaller increases in dose may be recommended by the investigators and sponsor upon consideration of all of the available clinical data.

If the first 2 subjects in a cohort experience a DLT, further enrollment to that cohort will stop and the BLRM will be updated with this new information. Re-evaluation of the available safety, PK, and PD data will occur. By incorporating information gained at the preceding dose levels, additional subjects may be enrolled at this dose level or a lower dose level as agreed by Investigators and Novartis personnel and if the BLRM predicts that the risk that this dose exceeds the MTD remains below 25% (EWOC).

Dose escalation will continue until identification of the MTD or a suitable lower RP2D. This will occur when the following conditions are met:

- at least 6 subjects have been treated at this dose and observed for two cycles
- this dose satisfies one of the following conditions:
 - 1. the posterior probability of targeted toxicity at this dose exceeds 50% and is the highest among potential doses, or
 - 2. Minimum of 12 subjects have already been treated on the trial.

It is the dose recommended for subjects, either per the model or by review of all clinical data by Novartis and investigators in a dose escalation teleconference, see Section 6.5.2.1.

To better understand the safety, tolerability and PK of siremadlin or rineterkib in combination with ruxolitinib, additional cohorts of subjects may be enrolled at preceding dose levels, or to intermediate dose levels before or while proceeding with further dose escalation.

If a decision is made to escalate to a higher dose level but one or more additional subject(s) treated at the preceding dose level experiences a DLT during the first cycle of treatment, then the BLRM will be updated with this new information before any additional subjects are enrolled at that higher dose level. Subjects ongoing will continue treatment at their assigned dose levels.

Crizanlizumab, sabatolimab and NIS793

For crizanlizumab, the dose level chosen to be evaluated in Arm 2 will be 5 mg/kg IV infusion Q4W (with the 2nd loading dose after 14 days of initial dosing for Cycle 1 only). For sabatolimab, the dose level chosen to be evaluated in Arm 3 will be 800 mg IV Q4W. For NIS793, the dose level chosen to be evaluated in Arm 5 will be 2100 mg IV O3W. If 2 subjects in any safety run-in arm (either Arm 2, Arm 3, or Arm 5) in Part 1 of the study experience a DLT within the first 2 cycles of study treatment, further enrollment into that arm will stop and that combination treatment will not open in Part 2.

A decision may be made to include further subjects into the combination arm or conduct additional dose cohorts within the arm based on a synthesis of all relevant data available in the ongoing study including safety information, DLTs, all CTCAE Grade > 2 toxicity data during Cycle 1 or 2, PK, and PD data from evaluable subjects. Any decisions will be made by Investigators and Novartis study personnel.

For Japan only: Further subjects can be added after the RP2D has been determined to further characterize safety.

6.5.2.1 Implementation of dose escalation decisions

To implement dose escalation decisions for siremadlin and rineterkib in combination with ruxolitinib, the available toxicity information (including adverse events and laboratory abnormalities that are not DLTs), the recommendations from the BLRM, and the available PK and PD information will all be evaluated by the Investigators and Novartis study personnel (including the study physician and statistician) during a dose decision meeting by teleconference. Drug administration at the next higher dose level may not proceed until the investigator receives written confirmation from Novartis indicating that the results of the previous dose level were evaluated and that it is permissible to proceed to a higher dose level.

6.5.2.2 Intra-Subject dose escalation

Intra-subject dose escalation is not allowed in this study.

6.5.3 Definitions of dose limiting toxicities (DLTs)

A dose-limiting toxicity (DLT) is defined as an adverse event or abnormal laboratory value assessed as clinically significant and considered by the Investigator to be related to siremadlin, crizanlizumab, sabatolimab, rineterkib, NIS793 as single contributors or in combination with ruxolitinib, that occurs within the first two cycles of treatment (C1D1 through to C3D1) of Part 1 and meets any of the criteria included in Table 6-4. Toxicities that are related to MF, MF progression, inter-current illness, or concomitant medications that occurs within the first two cycles of treatment (C1D1 through to C3D1) with ruxolitinib + siremadlin or ruxolitinib + crizanlizumab or ruxolitinib + sabatolimab or ruxolitinib + rineterkib or ruxolitinib + NIS793 will not be considered a DLT. The National Cancer Institute Common Terminology Criteria for Adverse events (NCI CTCAE) version 5.0 will be used for all grading. For the purpose of dose escalation decisions for the ruxolitinib + siremadlin and ruxolitinib + rineterkib combination treatments, DLTs will be considered and included in the BLRM.

The investigator must notify the sponsor immediately of any unexpected CTCAE grade ≥ 3 adverse events or laboratory abnormalities. Prior to enrolling subjects into a higher dose level, CTCAE grade ≥ 2 adverse events will be reviewed for all subjects at the current dose level.

Table 6-4 Criteria for defining dose-limiting toxicities (related to study treatment)

Toxicity	DLT Criteria
Hematologic toxicities	Acute severe myelosuppression in absence of leukemic transformation:
	Neutropenia G4*
	Febrile neutropenia G ≥ 3 (ANC < 1.0 x 10^9/L + Fever ≥ 38.5 degrees C)
	Thrombocytopenia G4* (platelets < 25 x 10^9/L) persisting ≥ 3 days
	Prolonged myelosuppression in absence of leukemic transformation:
	Thrombocytopenia G3 (platelets < 50 x 10^9/L) persisting ≥ 21 days
	Thrombocytopenia G3 (platelets < 50 x 10^9/L) prior to dosing on C2D1 and C3D1 **
Non-hematologic toxicities	All toxicity ≥ Grade 3 not due to underlying MF or complications of the disease (for all arms)
	Other Toxicity < Grade 3 considered as DLTs for subjects on arms containing rineterkib:
	Retinal vein occlusion of any CTCAE Grade confirmed by ophthalmologic evaluation
	Newly emerging grade 2 total bilirubin with ≥ CTCAE Grade 2 AST/ALT
	Other Toxicity < Grade 3 considered as DLTs for subjects on arms containing NIS793:
	Grade 2 bullous disease that does not resolve to ≤ Grade 1 within 7 days of starting corticosteroids

^{*} in two consecutive assessments within 24 hours (the second assessment will be considered valid and final)

**in case of platelets count of 40,50 x 10/9/l. the assessment has to be repeated within 24 hours. The secon

6.5.4 Dose modifications

For subjects who do not tolerate the protocol-specified dosing schedule due to DLT or other toxicities, dose adjustments are permitted in order to allow subjects to continue the study treatment. Similar guidelines also apply to the extension treatment phase. All dose modifications should be based on the worst preceding toxicity and AEs are to be graded

^{**}in case of platelets count of 40-50 x 10^9/L, the assessment has to be repeated within 24 hours. The second assessment will be considered valid and final CTCAE version 5.0 will be used for all grading

according to NCI CTCAE v5.0. If the investigational study treatment is being held due to toxicity, planned visits and all assessments should continue as scheduled, except without dosing.

For Part 1, dose modifications for toxicities occurring during the DLT-definition period (i.e. first 2 cycles of treatment C1D1 through C3D1), and considered as treatment-related, will not be allowed unless the toxicity qualifies as DLT. After a toxicity has been characterized as a DLT, a subject can resume therapy with a modified dose according to the guidelines.

During part 2 and 3, investigator should follow the dose modifications for toxicities during any cycle of the treatment period.

These dose changes must be recorded on the appropriate eCRF.

For clinical management of suspected immune-related events for sabatolimab and NIS793, reference to consensus management guidelines is recommended, such as those provided in the NCCN Guidelines for the Management of Immunotherapy-Related Toxicities (NCCN Guidelines for specific populations), ASCO clinical practice guideline for Management of Immune-Related Adverse Events in Patients Treated With Immune Checkpoint Inhibitor Therapy (Brahmer et al 2018) or the ESMO Clinical Practice Guidelines for Management of Toxicities from Immunotherapy (Haanen et al 2017). Note that in general, sabatolimab or NIS793 should be interrupted for grade 3 and 4 toxicities and for a subset of lower grade toxicities. If the specific adverse event is not listed, the guideline for "Other adverse events" must be followed. Deviations to mandatory dose interruptions and/or reductions are not allowed. Permanent treatment discontinuation is mandatory for specific events

The investigator should follow the dose modifications for the study drug suspected to be related to the event:

- If the event is suspected to be related to ruxolitinib, the investigator should follow the dose modification specific to ruxolitinib as per current label. If the event is suspected to be related to siremadlin, crizanlizumab, sabatolimab, rineterkib or NIS793, the investigator should follow the dose modifications specific for the suspected study drug.
- In the occurrence of potentially overlapping toxicity or if it cannot be distinguished which
 of the study drugs within the combination is suspected to be related to the event, the
 investigator should first modify the dose of siremadlin, crizanlizumab, sabatolimab,
 rineterkib or NIS793 before changing the ruxolitinib dose. If the toxicity does not resolve
 until the next planned dose of siremadlin, crizanlizumab, sabatolimab, rineterkib or NIS793,
 the investigator should follow the dose modifications specific to both study drugs within the
 combination treatment.

[figure not shown]
Additionally, the following guidelines need to be considered for patients on siremadlin and rineterkib:

[figure not shown]
- A patient must discontinue treatment with siremadlin or rineterkib if, after treatment is resumed at a lower dose, the toxicity recurs with the same or worse severity, unless in the opinion of the investigator it is in the patient's best interest to continue siremadlin or rineterkib, and upon documented agreement with Novartis.
- For each patient, once a dose reduction has occurred, the dose level must not be re-escalated during subsequent treatment cycles with siremadlin or rineterkib.

Finally, the following guidelines should be followed for patients on NIS793:

- No dose reductions are allowed for NIS793. Reducing dosing frequency is allowed under circumstances
- Dose interruption due to toxicities is permitted. Dosing of study treatment may resume once the AE has resolved,

[figure not shown]

[figure not shown]

[figure not shown]
Confidential

[figure not shown]
Novartis

[figure not shown]

[figure not shown]

[figure not shown]

[figure not shown]

6.5.4.1 Dose adjustments for QTcF prolongation

In case QTcF prolongation > 500 msec (or QTcF prolongation > 60 msec from baseline) is observed at any time point during study treatment, and confirmed, increased ECG safety monitoring is mandatory during or in-between subsequent visits (e.g. collecting ECGs at following treatments at predose and at Cmax), as follows:

Collect triplicate ECG and confirm QTc assessment (by site cardiologist or Novartis cardiologist)

Page 128 of 267

- Correct any serum electrolyte abnormalities (in particular hypokalemia, hypomagnesemia) before continuing study treatment.
- Review concomitant medication use for other causes for QT prolongation (refer to qtdrugs.org for known QT prolonging drugs) and for drugs with the potential to increase the risk of drug exposure related QT prolongation (e.g. concomitant use of CYP3A4 inhibitors, if the study treatment is a CYP3A4 substrate)
- Check the dosing schedule and treatment compliance
- Consider collecting a time-matched PK sample (Refer to PK sampling section for correct procedures) and record time and date of last study treatment intake. Not applicable during the extension treatment phase.

6.5.5 Follow-up for toxicities

Subjects whose treatment is interrupted or permanently discontinued due to an adverse event or clinically significant laboratory value, must be followed up at least once a week (or more frequently if required by institutional practices, or if clinically indicated) for 4 weeks, and subsequently at approximately 4-week intervals, until resolution or stabilization of the event, whichever comes first. Similar guidelines apply during the extension treatment phase. Appropriate clinical experts such as cardiologist, dermatologist, psychiatrists, etc., should be consulted as deemed necessary. All subjects must be followed up for adverse events and serious adverse events (SAEs) for 30 days after the last dose of single-agent ruxolitinib (control/monotherapy), for 30 days after the last dose of ruxolitinib or siremadlin for subjects on ruxolitinib + siremadlin (or siremadlin monotherapy in Part 3), for 30 days after the last dose of ruxolitinib or rineterkib for subjects on ruxolitinib + rineterkib (or rineterkib monotherapy in Part 3), for 90 days after the last dose of NIS793 for subjects on ruxolitinib + NIS793 (or NIS793 monotherapy in Part 3), for 105 days after the last dose of crizanlizumab for subjects on ruxolitinib + crizanlizumab (or crizanlizumab monotherapy in Part 3), and for 150 days after the last dose of sabatolimab for subjects on ruxolitinib + sabatolimab (or sabatolimab monotherapy in Part 3).

Follow up for Siremadlin 6.5.5.1

For subjects receiving siremadlin, Table 6-10 outlines the follow-up evaluations recommended for toxicities of specific types and CTCAE grades.

Table 6-10 Follow-up evaluations for selected toxicities

Toxicity	Follow-up Evaluation
Blood and lymphatic system disorders	Test twice weekly until ≤ CTCAE grade 2, then restart treatment Continue to test weekly until resolution to baseline or stabilization.
Investigations (hematologic)	Test twice weekly until ≤ CTCAE grade 2, then restart treatment
Neutropenia ≥ CTCAE	Continue to test weekly until resolution to baseline or stabilization.
grade 3	Perform physical examination for check on bruising in case of major thrombocytopenia.

Toxicity	Follow-up Evaluation
Thrombocytopenia ≥ CTCAE grade 3	
Investigations (metabolic)	Test twice weekly until ≤ CTCAE grade 2, then restart treatment
Amylase or lipase ≥	Continue to test weekly until resolution to ≤ CTCAE grade 1 or stabilization.
CTCAE grade 3	A CT scan or equivalent imaging procedure to assess the pancreas, liver, and gallbladder is recommended within 7 days of the first occurrence of any ≥ CTCAE grade 3 result, to exclude disease progression or potential other liver disease.
	In subjects with serum triglycerides ≥ 500 mg/dL, urine amylase also needs to be tested.
Cardiac disorders	Refer to ECG and QTc Clinical Safety Standards Guidelines
QT and ECG	Twice weekly ECGs until normalization or stabilization of ECG findings then restart
ECG changes indicative of ischemic event	treatment refer to section 6.5.4.1.

6.5.5.2 Follow up for sabatolimab & NIS793

The emergence of Immune-Related AE (irAE) may be anticipated based on general experience in clinical studies with similar class of compounds that block the negative immune regulators.

An irAE is a clinically significant AE affecting any organ that is associated with study drug exposure, is consistent with an immune-mediated mechanism, and where alternative explanations have been investigated and ruled out or are considered unlikely.

Subjects should be monitored carefully for any skin toxicity or mucositis and study treatment should be discontinued for any suspected case of SJS/TEN.

Serologic, histologic and immunological assessments should be performed as deemed appropriate by the Investigator, to verify the immune-related nature of the AE.

All subjects with signs or symptoms of irAEs should be monitored and managed following the consensus guidelines from NCCN, ASCO or ESMO for the management of immune-related adverse events as outlined in Section 6.5.4

Patients whose treatment is interrupted or permanently discontinued due to an irAE, AE or clinically significant laboratory value, must be followed-up at least once a week (or more frequently if required by institutional practices, or if clinically indicated) for 4 weeks, and subsequently at approximately 4-week intervals, until resolution or stabilization of the event, whichever comes first. Appropriate clinical experts should be consulted as deemed necessary.

In case of a suspected irAE, the relevant immunological assessments (e.g. rheumatoid factor, anti-DNA Ab, etc.) should be performed. In case of a toxicity suspected to be a cytokine release syndrome, the assessments outlined in Section 8 (Table 8-2, Table 8-3, Table 8-4 & Table 8-5) must be performed. All patients must be followed up for irAEs, AEs and SAEs for 90 days following the last dose of NIS793 in combination with ruxolitinib, and for 105 days following the last dose of sabatolimab in combination with ruxolitinib.

For any AE/AEs Grade 1 and/or Grade 2, treatment with sabatolimab should be maintained at the determined dose and schedule, unless otherwise specified in Table 6-7. Similarly,

For any AE/AEs Grade 1 and/or Grade 2, treatment with NIS793 should be maintained at the determined dose and schedule, unless otherwise specified in

Follow up on potential drug-induced liver injury (DILI) cases

Subjects with transaminase increase combined with TBIL increase may be indicative of potential DILI and should be considered as clinically important events.

The threshold for potential DILI may depend on the subject's baseline AST/ALT and TBIL value; subjects meeting any of the following criteria will require further follow-up as outlined below:

- For subjects with normal ALT and AST and TBIL value at baseline: AST or ALT > 3.0 xULN combined with TBIL > 2.0 x ULN
- For subjects with elevated AST or ALT or TBIL value at baseline: [AST or ALT > 2 xbaseline AND > 3.0 x ULN] OR [AST or ALT > 8.0 x ULN], combined with [TBIL > 2 x baseline AND > 2.0 x ULN

Medical review needs to ensure that liver test elevations are not caused by cholestasis, defined as ALP elevation > 2.0 x ULN with R value < 2 in subjects without bone metastasis, or elevation of ALP liver fraction in subjects with bone metastasis.

Note: The R value is calculated by dividing the ALT by the ALP, using multiples of the ULN for both values. It denotes whether the relative pattern of ALT and/or ALP elevation is due to cholestatic ($R \le 2$), hepatocellular ($R \ge 5$), or mixed (R > 2 and < 5) liver injury.

In the absence of cholestasis, these subjects should be immediately discontinued from study treatment, and repeat LFT testing as soon as possible, preferably within 48 hours from the awareness of the abnormal results. The evaluation should include laboratory tests, detailed history, physical assessment, and the possibility of liver metastasis or new liver lesions, obstructions/compressions, etc.

- 1. Laboratory tests should include ALT, AST, albumin, creatine kinase, total bilirubin, direct and indirect bilirubin, GGT, prothrombin time (PT)/INR, and alkaline phosphatase.
- 2. A detailed history, including relevant information, such as review of ethanol, concomitant medications, herbal remedies, supplement consumption, and history of any pre-existing liver conditions or risk factors, should be collected.
- 3. Further testing for acute hepatitis A, B, C or E infection and liver imaging (e.g. biliary tract) may be warranted.
- 4. Obtain PK sample, as close as possible to last dose.
- 5. Additional testing for other hepatotropic viral infection (CMV, EBV or HSV), autoimmune hepatitis or liver biopsy may be considered as clinically indicated or after consultation with specialist/hepatologist.

All cases confirmed on repeat testing meeting the laboratory criteria defined above, with no other alternative cause for LFT abnormalities identified, should be considered as "medically significant," (Table 6-11) and thus, meet the definition of SAE and should reported as SAE using the term "potential drug-induced liver injury." All events should be followed up with the outcome clearly documented.

Table 6-11 Guidance to rule out possible alternative causes of observed LFT abnormalities

Disease	Assessment
Hepatitis A, B, C, E	• IgM anti-HAV; HBsAg, IgM & IgG anti-HBc, HBV DNA; anti-HCV, HCV RNA, IgM & IgG anti-HEV, HEV RNA
CMV, HSV, EBV infection	• IgM & IgG anti-CMV, IgM & IgG anti-HSV; IgM & IgG anti- EBV
Autoimmune hepatitis	Antinuclear Antibodies (ANA) & Anti-Smooth Muscle Antibody (ASMA) titers, total IgM, IgG, IgE, IgA
Alcoholic hepatitis	• Ethanol history, GGT, Mean Corpuscular Volume (MCV), CD-transferrin
Nonalcoholic steatohepatitis	Ultrasound or MRI
Hypoxic/ischemic hepatopathy	 Medical history: acute or chronic congestive heart failure, hypotension, hypoxia, hepatic venous occlusion. Ultrasound or MRI.
Biliary tract disease	Ultrasound or MRI, Endoscopic retrograde cholangiopancreatography (ERCP) as appropriate.
Wilson disease (if <40 yrs old)	Caeruloplasmin
Hemochromatosis	Ferritin, transferrin
Alpha-1-antitrypsin deficiency	Alpha-1-antitrypsin

Other causes should also be considered based upon participants' medical history (hyperthyroidism / thyrotoxic hepatitis – T3, T4, TSH; cardiovascular disease / ischemic hepatitis – ECG, prior hypotensive episodes; Type 1 diabetes / glycogenic hepatitis).

Following appropriate causality assessments, as outlined above, the causality of the treatment is estimated as "probable" i.e. >50% likely, if it appears greater than all other possible causes of liver injury combined. The term "treatment-induced" indicates probably caused by the treatment, not by something else, and only such a case can be considered a DILI case and should be reported as an SAE.

All cases confirmed on repeat testing meeting the laboratory criteria defined above, with no other alternative cause for LFT abnormalities identified, should be considered as "medically significant," and thus, meet the definition of SAE and should be reported as SAE using the term "potential treatment-induced liver injury." All events should be followed up with the outcome clearly documented.

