All reports of intentional misuse and abuse of the product are also considered serious adverse event irrespective if a clinical event has occurred (Section 10.1.5).

Treatment-emergent elevations in AST or ALT (>3x ULN) in combination with total bilirubin >2x ULN or jaundice in the absence of cholestasis (defined as ALP < 2 ULN) or other causes of hyperbilirubinemia can be an indicator of severe drug induced liver injury (Hy's Law).

For this reason, a potential Hy's Law case requires expedited reporting, and will be handled as a serious unexpected adverse event (assessing it as medically significant in the absence of any other seriousness criteria). It must be reported as an SAE to the sponsor promptly (i.e., even before all other possible causes of liver injury have been excluded). Reporting should include all available information, especially that needed for evaluating the diagnosis, severity and likelihood that the study treatment caused the reaction. For patient monitoring and to better understand potential etiologies, the investigator must initiate a close follow-up until complete resolution of the problem and completion of all attempts to obtain supplementary data.

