10.1.3 SAE reporting

To ensure subject safety, every SAE, regardless of causality, occurring after the subject has provided informed consent must be reported to Novartis safety immediately, without undue delay, but under no circumstances later than within 24 hours of obtaining knowledge of the events (Note: If more stringent, local regulations regarding reporting timelines prevail) until the end of the safety follow-up period, as follows:

- 30 days after the last dose of single-agent ruxolitinib (control/monotherapy)
- 30 days after the last dose of ruxolitinib or siremadlin for subjects on ruxolitinib + siremadlin (or siremadlin monotherapy in Part 3)
- 30 days after the last dose of ruxolitinib or rineterkib for subjects on ruxolitinib + rineterkib (or rineterkib monotherapy in Part 3)
- 90 days after the last dose of NIS793 for subjects on ruxolitinib + NIS793 (or NIS793 monotherapy in Part 3)
- 105 days after the last dose of crizanlizumab for subjects on ruxolitinib + crizanlizumab (or crizanlizumab monotherapy in Part 3),
- 150 days after the last dose of sabatolimab for subjects on ruxolitinib + sabatolimab (or sabatolimab monotherapy in Part 3).

If a subject starts post treatment anti-neoplastic medication then only SAEs suspected to be related to study treatment should be collected, up to the time frame noted above depending on the study treatment (30 days for ruxolitinib, siremadlin or rineterkib, 90 days for NIS793, 105 days for crizanlizumab or 150 days for sabatolimab).

For Screen Failure subjects, SAEs occurring after the subject has provided informed consent until the time the subject is deemed a Screen Failure must be reported to Novartis.

Detailed instructions regarding the submission process and requirements are to be found in the investigator folder provided to each site.

All follow-up information for the SAE including information on complications, progression of the initial SAE and recurrent episodes must be reported as follow-up to the original episode immediately, without undue delay, but under no circumstances later than within 24 hours of the investigator receiving the follow-up information (Note: If more stringent, local regulations regarding reporting timelines prevail). An SAE occurring at a different time interval or otherwise considered completely unrelated to a previously reported one must be reported separately as a new event.

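### Protocol 6.5.5.3 makes the SAE report of a liver signal wait for confirmation and causality, 10.1.2 requires a potential Hy's Law case to be reported before other causes are excluded, and no sentence says which governs

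*Protocol*

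**What the plan says.** Three places in the Protocol govern the report.

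**Section 6.5.5.3** (follow-up of potential drug-induced liver injury) sets the laboratory trigger. For normal baseline values it is AST or ALT above 3.0 x ULN with total bilirubin above 2.0 x ULN; for elevated baselines it is adjusted. Medical review must ensure that the elevation is "not caused by cholestasis, defined as ALP elevation > 2.0 x ULN with R value < 2" (in subjects without bone metastasis). Repeat testing follows as soon as possible, preferably within 48 hours. The section then gives two routes to an SAE:

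- "All cases confirmed on repeat testing meeting the laboratory criteria defined above, with no other alternative cause for LFT abnormalities identified" are to be considered medically significant and reported as SAEs. This appears twice, with two different SAE terms.
- After the Table 6-11 work-up, causality is probable if treatment is more than 50% likely, that is, greater than all other causes combined. The text then states that "only such a case can be considered a DILI case and should be reported as an SAE".

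**Section 10.1.2** defines a potential Hy's Law case as a treatment-emergent AST or ALT above 3 x ULN with total bilirubin above 2 x ULN or jaundice, "in the absence of cholestasis (defined as ALP < 2 ULN) or other causes of hyperbilirubinemia". On timing: "It must be reported as an SAE to the sponsor promptly (i.e., even before all other possible causes of liver injury have been excluded".

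**Section 10.1.3** requires that "every SAE, regardless of causality, occurring after the subject has provided informed consent must be reported to Novartis safety immediately", and "under no circumstances later than within 24 hours of obtaining knowledge of the events". Later information "must be reported as follow-up to the original episode immediately".

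**The concern.** For one and the same signal, 6.5.5.3 places the SAE report after confirmation and attribution, while 10.1.2 places it before attribution. Neither section cites the other.

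Both texts apply to the same people. Section 6.5.5 says that similar guidelines apply in the extension phase, and the Amendment 9 list of changes has an entry for 10.1.2 but none for 6.5.5.3. The stated purpose of the addition (Amendment 9 list; SAP Section 1) was expedited reporting of potential Hy's Law cases at the FDA's request. The section a site would naturally open for a liver signal still carries the older, exclusive wording.

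At stake is a potential Hy's Law case that is reported late or, if another cause turns up during the work-up, not reported under the liver pathway at all.

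**Working it through.** The plan gives no figure to reproduce, so this is a comparison of texts with a few threshold checks. All values are multiples of ULN.

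**Step 1: do the two definitions overlap?** Take a normal baseline, ALT 4, bilirubin 2.5, ALP 1.2, a treatment-emergent rise and no known other cause of hyperbilirubinemia (hypothetical values).

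- 6.5.5.3: 4 > 3, 2.5 > 2, and ALP is not above 2, so not cholestasis. Met.
- 10.1.2: 4 > 3, 2.5 > 2, ALP 1.2 < 2. Met.

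One subject can therefore fall under both rules.

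**Step 2: what does each rule say for that subject?**

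| | 6.5.5.3 | 10.1.2 with 10.1.3 |
|---|---|---|
| Repeat confirmation | condition of the first SAE route | not mentioned |
| Alternative causes | none identified (first route), or treatment outweighs them all (second route) | report before they have been excluded |
| Causality | over 50% likely, with exclusive wording | report regardless of causality |
| Time limit for the report | none stated | promptly; 24 hours from awareness |

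**Step 3: is there a tie-breaker?** I looked at each mention of Hy's Law or DILI in the Protocol and the SAP and found no statement of precedence. Section 10.1.3 applies to every SAE but names neither 6.5.5.3 nor Hy's Law. A site working from 6.5.5.3 could conclude that there is no SAE yet and that the 24-hour limit has not started.

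**Step 4: do the definitions coincide everywhere?** They do not, and this matters for the fix.

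- *Only the 10.1.2 thresholds met.* Baseline ALT 2.0 (Section 5.2 excludes only above 2.5), normal baseline bilirubin; then ALT 3.5, bilirubin 2.5, ALP 1.0. The rise is 3.5 / 2.0 = 1.75 times baseline, below 2, and 3.5 is below 8. The 6.5.5.3 trigger is not met.
- *Only 6.5.5.3 met.* Normal baseline, ALT 10, bilirubin 3, ALP 2.5. R = 10 / 2.5 = 4, not below 2, so 6.5.5.3 does not call it cholestasis. ALP is not below 2, so it lies outside 10.1.2.

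**Step 5: can the SAE clause in the exclusive sentence simply be deleted?** Take the second case in Step 4 and add a lesser competing cause, with treatment still judged more than 50% likely. The first route fails because an alternative cause has been identified. Section 10.1.2 fails on ALP. The exclusive sentence is then the only liver-specific SAE instruction left. Deleting its reporting clause would leave only the general seriousness criteria of 10.1.2.

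**Step 6: how many subjects?** The Hy's Law text came with Amendment 9, after enrollment had been halted. SAP 1.1 puts the maximum entering the extension at 4, and the Amendment 8 rationale counts 4 ongoing on 05-Oct-2022.

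**The case against.** The strongest reply is that the documents already answer the question and lack only a cross-reference. Section 10.1.2 says that a potential case must be reported, and it addresses the very condition that 6.5.5.3 imposes, the exclusion of other causes. Section 6.5.5.3 says its cases meet the definition of an SAE, and 10.1.1 places that definition in 10.1.2. Sections 9.2 and 10.1.1 send serious events to Section 10. The two sentences on confirmed cases give sufficient conditions, and nothing in 6.5.5.3 tells a site to withhold a report. SAP 2.8.3 tabulates ALT or AST above 3 x ULN with bilirubin above 2 x ULN and ALP below 2 x ULN from laboratory values, so that table does not depend on the SAE route.

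Most of this stands. A reader might infer that the sections give opposite instructions, so that complying with one breaks the other. The documents do not support that: a site that reports at once and sends repeat tests and work-up as follow-up satisfies both. The contrast is also narrower than it first looks, because the 10.1.2 definition itself excludes cholestasis and other causes of hyperbilirubinemia.

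What the reply does not remove is the word *only*. Taken literally, the exclusive sentence limits SAE reporting to cases already attributed to treatment, and nothing in 6.5.5.3 points the reader to the later rule.

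**Conclusion.** The point holds as a conflict of wording on safety reporting for a signal that meets both definitions, with no stated precedence. The documents lean towards Section 10. A late or missing report is possible for a site that relies on 6.5.5.3 alone; it is not certain.

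The size is small in numbers: at most 4 extension subjects, and the documents do not say whether any has elevated baseline values. A reader might subtract the 24-hour limit from the 48-hour repeat test and conclude that reports would be 24 hours late. The documents do not support that figure. The 48 hours is a preference, neither a maximum nor an expected time; the alternative-cause work-up has no time limit; and if 6.5.5.3 is read alone, the limit has not yet started to run. No delay can be quantified.

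The conclusion assumes a normal baseline, absence of cholestasis under both definitions, a treatment-emergent rise and no known other cause of hyperbilirubinemia. Outside that overlap the two definitions diverge, and the conflict does not arise in the same form.

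**What to change.** In 6.5.5.3, before the first of the two sentences on confirmed cases, insert:

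> *Any case meeting the potential Hy's Law definition in Section 10.1.2 is reported as an SAE under Sections 10.1.2 and 10.1.3 within 24 hours of awareness, whatever the status of repeat testing, Table 6-11 work-up or causality; these are sent as follow-up information. This takes precedence over the conditions below.*

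In the exclusive sentence, keep the part that reserves the DILI label for probable cases, and replace the reporting clause after it with: *it should be reported as an SAE if not already reported under Section 10.1.2*. Exclusivity then applies to classification alone, and the SAE route in Step 5 survives. Leave both sentences on confirmed cases in place as the route for cases outside 10.1.2.

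Separately, the sponsor must reconcile the definitions in 6.5.5.3 and 10.1.2 (cholestasis by ALP with R value or by ALP alone, baseline adjustment, jaundice, treatment-emergent onset, other causes of hyperbilirubinemia) and the two SAE terms in 6.5.5.3. No clinical definition is proposed here.

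The cost is one short insertion, one reworded clause and possibly a few SAE reports, from at most 4 subjects, that are later attributed to other causes. Section 10.1.2 already accepts that cost by asking for early reports. Reconciling the definitions is further work, but the insertion need not wait for it.
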